12.4 Safety Analysis

12.4.1 Adverse Event

The frequency of toxicities will be tabulated by maximum grade by preferred term within a patient across all cycles. All participants who receive any study treatment will be considered evaluable for toxicity.

12.5 Phase Ib Analysis and Criteria for Early Termination of the Study

There will be an initial Phase Ib cohort to examine the safety and tolerability of the combination. After up to nine patients are enrolled, and at least 6 have completed at least two cycles of chemotherapy, the study will be suspended, and the safety/tolerability of the combination will be examined. If ≥ 2 patients out of 6 (or $\geq 2/7$, $\geq 2/8$, or $\geq 3/9$) patients have DLTs, the study will be modified or stopped after review of all safety data. The Roswell Phase I Committee, Study PI, and study statistician will all be involved in the discussion. At that time, the study team will decide what action to take, e.g., continue the study as is, make changes to the study with regard to treatment or dose modifications, or discontinue the study. Should the study team elect to continue the study with additional modifications, the revised protocol must be submitted to the FDA for further review prior to implementation in the clinical study.

The dose limiting toxicity (DLT) will be defined as any \geq grade 3 clinically significant toxicity, which is deemed possibly treatment related and occurs within the first 6 weeks of therapy. This will be exclusive of rash, fatigue and hypomagnesemia, but inclusive of grade 4 rash or hypomagnesemia which does not revert to grade ≤ 2 within 24 hours.

Following the phase Ib cohort, no interim analyses for efficacy are planned for this study. The study adds an agent (pembrolizumab) to a standard of care agent (cetuximab), so we expect efficacy to be at least as good as standard of care.

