Objectives	
Primary:
 
 To estimate the objective response rate of patients with metastatic colorectal cancer treated with pembrolizumab and cetuximab. To estimate the 6-month progression-free survival (PFS) rate of patients with metastatic colorectal cancer treated with pembrolizumab and cetuximab. To examine the adverse event profile of combining pembrolizumab and cetuximab. 
Secondary:
 
 To examine the PFS of patients with metastatic colorectal cancer treated with pembrolizumab and cetuximab. To determine the objective response rate by immune-related response criteria (irRECIST) of patients with metastatic colorectal cancer treated with pembrolizumab and cetuximab To examine the overall survival of patients with metastatic colorectal cancer treated with pembrolizumab and cetuximab. 
Exploratory:
 
 To identify tumor and peripheral blood biomarkers of response and/or resistance to the study treatment.
Study Design	Phase Ib/II study, single arm, multi-institutional study.
Target Accrual and Study Duration	We will target 42 eligible and treated patients, but will require at least 38 eligible and treated patients. An initial 9 patient phase Ib study is planned to ensure safety of the combination. This will be followed by further enrollment of 33 patients on the phase II study. It is expected that this study will enroll 1-2 patients per month. With this accrual rate, this study is anticipated to finish accrual in 4 years. Assuming a minimum of 6 months of follow-up in all patients, the study will take 4 years to complete in total.
Study Procedures	
Disease Evaluation: CT chest/abd/pelvis (or acceptable alternative) every 9 weeks (+/- 7 days)
 
Physical Examination (including vital signs, and body weight): Baseline, Day 1 of all Cycles, End of Treatment, Safety Follow-Up

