4.1.1 Phase Ib\II

There will be an initial phase Ib cohort to examine the safety and tolerability of the combination. Study progress will be monitored regularly by the RPCI Phase I Committee. After up to 9 patients are enrolled, and a minimum of 6 have completed at least two cycles of chemotherapy, the study will be suspended, and the safety/tolerability of the combination will be examined. At that time, the study team will decide what action to take, e.g., continue the study as is, make changes to the study with regard to treatment or dose modifications, or discontinue the study. Once analysis is complete and a safe treatment plan has been established, the phase II study will commence.

The Phase II study will enroll patients with metastatic colorectal cancer who are eligible for anti-EGFR therapy (i.e. RAS wt, no known expanded KRAS or NRAS mutations, anti-EGFR therapy naïve or appropriate for anti-EGFR rechallenge). For the purposes of the study, a cycle will be defined as three weeks. Patients will be treated with cetuximab, administered weekly and pembrolizumab, administered every 3 weeks as described in **Section 6**. A regimen of pre-emptive skin care is recommended, as described in **Section 6.4**. Disease assessments will occur every 9 weeks to assess response, using RECIST v 1.1. As described in **Section 6.1**, after initial progressive disease, if fulfilling certain criteria, patients may continue on therapy with further response assessments in line with irRECIST criteria (**Appendix D**). Per local policy, a consent addendum should be obtained to continue on treatment past progression. Progression free survival and objective response rate will be observed. Additional blood based biomarker tests will be performed prior to treatment, at 4 weeks (cycle 2, day 1) and 10 weeks (cycle 4, day 1). A mandatory biopsy will be performed prior to treatment; a secondary biopsy at approximately 10 weeks (cycle 4, day 1) will be optional, but strongly encouraged. However, in order to obtain sufficient samples for informative analysis, for the final 10 patients of the study, both biopsies will be mandatory.

Primary Endpoints

- Six-month progression free survival and objective tumor response rate will be evaluated according to RECIST 1.1 guidelines after every 3 cycles (9 weeks) of treatment.

- Adverse events will be categorized and graded according to NCI CTCAE v4.0.

Secondary Endpoints

- Progression-free survival
- Overall survival

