11 DATA AND SAFETY MONITORING

The RPCI Data and Safety Monitoring Board will assess the progress of the study, the safety data, and critical efficacy endpoints. During the Phase Ib study, the study conduct will be reviewed by the RPCI Phase I Committee on a weekly basis. The DSMB will review the study annually and will make recommendations that include but not limited to; (a) continuation of the study, (b) modifications to the design (c) or termination of the study.

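### The formal phase Ib safety review waits for six patients to complete two cycles and has no DLT trigger, so early toxic dropout delays it and three DLTs require no pause

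*Combined protocol and SAP*

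**What the plan says.** The synopsis gives the purpose: "An initial 9 patient phase Ib study is planned to ensure safety of the combination". Section 12.5 sets the timing. "After up to nine patients are enrolled", and when "at least 6 have completed at least two cycles of chemotherapy, the study will be suspended", safety and tolerability are examined. Section 4.1.1 has the same trigger: "a minimum of 6 have completed at least two cycles of chemotherapy, the study will be suspended".

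The DLT limits follow in 12.5: if at least 2 of 6, 2 of 7, 2 of 8 or 3 of 9 "patients have DLTs, the study will be modified or stopped after review of all safety data". A DLT is an event that "occurs within the first 6 weeks of therapy". Section 4.1.1 says "a cycle will be defined as three weeks", so two cycles span the DLT window.

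Other oversight is described elsewhere. Section 11 says that during phase Ib "the study conduct will be reviewed by the RPCI Phase I Committee on a weekly basis". Section 16.2 lets the institution terminate at any time for safety. Section 4.1.1 makes the start of phase II conditional on the analysis being complete and a safe plan being in place. Section 12.4.1 counts anyone who received any study treatment as evaluable for toxicity.

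**The concern.** The event that starts the formal review is treatment completion, which becomes rarer as toxicity rises. A patient taken off treatment in the first six weeks contributes to the toxicity count but not clearly to the six completers. The more early toxicity there is, the later the review falls, and with enough of it the condition cannot be met in nine patients.

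The DLT limits are applied only at that review. A count that meets all of them can therefore be reached with no stated consequence while enrollment remains open. At stake is the exposure of up to six further patients in a lead-in that exists to protect them, for a combination on which section 1.5 reports no published data in this disease.

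**Working it through.** The plan gives no error rate or other operating characteristic for the phase Ib rule, so there is no figure to reproduce.

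**Inputs from the protocol.** Cohort cap 9; trigger 6 completers of two cycles; limits 2/6, 2/7, 2/8, 3/9 (12.5); DLT window 6 weeks (12.5); cycle 3 weeks (4.1.1); accrual 1 to 2 patients per month (synopsis).

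**Assumed, because the protocol gives neither.** DLT rate 20% or 1/3; probability q of not completing two cycles, for any reason, from 10% to 40%.

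**Step 1. Which count meets every limit.** Three DLTs meet 2/6, 2/7, 2/8 and 3/9. Two DLTs meet the first three but not 3/9. The earliest that three can occur is in the first three patients, leaving 9 − 3 = 6 who may still enter.

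**Step 2. Trigger delayed.** If any of the first six does not complete, a seventh patient or more is needed: P = 1 − (1 − q)^6.

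**Step 3. Trigger unreachable.** With nine patients, four or more non-completers leave at most five completers: P = 1 − Σ C(9,k) q^k (1 − q)^(9−k), k = 0 to 3. At q = 0.20 this is 1 − (0.1342 + 0.3020 + 0.3020 + 0.1762) = 0.0856.

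| q | Delayed: at least 1 of first 6 does not complete | Unreachable: fewer than 6 of 9 complete |
|---|---|---|
| 10% | 47% | 0.8% |
| 20% | 74% | 8.6% |
| 1/3 | 91% | 35% |
| 40% | 95% | 52% |

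**Step 4. How q depends on an undefined term.** Let p be the DLT rate, c the share of DLT patients who still complete two cycles, and 10% the assumed dropout among the others. Then q = p(1 − c) + 0.10(1 − p). At p = 0.20, q is 0.28, 0.18 or 0.08 for c = 0, 0.5 or 1. At p = 1/3, q is 0.40, 0.23 or 0.07. The range is wide because the plan does not say whether a patient who stops one drug and continues the other has completed a cycle.

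**Step 5. Patients entering after a third DLT.** Simulation with the six-completer suspension in place: Poisson accrual at 1 or 2 per month, DLT time uniform over 42 days, cap of 9, 10% other dropout, c from 0 to 1. The figures are over all cohorts, not only those with three DLTs.

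| DLT rate | At least one patient enters after the third DLT | Mean number per cohort |
|---|---|---|
| 20% | roughly 10 to 17% | 0.2 to 0.4 |
| 1/3 | 29 to 47% | 0.7 to 1.3 |

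**The case against.** The strongest reply is that other oversight fills the gap. The Phase I Committee reviews conduct weekly (section 11), SAEs reach the sponsor within 24 hours (10.2.2, 10.4), AEs of all grades and attributions are reported in phase 1 (10.1.3, Table 8), network sites must confirm an open slot before each phase 1 consent (Appendix A), and the institution can terminate at any time (16.2). This stands as far as it goes: any of these could stop enrollment early. None states a DLT count at which early action is due, so the safeguard is discretionary.

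A reader might infer that enrollment must continue after a failing count, or that in the most toxic cohorts no safety review occurs. The documents support neither. They permit continued enrollment without requiring it. What slips is the formal suspension review, and if it is never triggered, phase II cannot open (4.1.1). Exposure is bounded by the cohort of nine.

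A reader might also infer that patients entering after the third DLT add nothing, since the outcome is fixed. That is not so. Section 12.5 says the study will be modified or stopped when a limit is met, but then lists continuing unchanged among the options. Later patients would inform that choice.

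Finally, the higher non-completion rates have no support in the protocol. First restaging is at 9 weeks, after the two cycles (8.3); treatment may continue past initial progression (6.5); and one drug may continue when the other is stopped (6.1). Against this, Table 1 in 6.1.1 permanently discontinues pembrolizumab for several grade 3 to 4 events, so toxicity and non-completion are linked. The size is uncertain in both directions.

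**Conclusion.** The point holds as a flaw in the stated rule, limited to the formal review. The trigger in 12.5 and 4.1.1 has no toxicity component, moves later as early toxic dropout rises, and has no provision for fewer than six completers. Three DLTs meet every limit the sponsor has set, yet neither pause enrollment nor bring the review forward.

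The size rests on assumed rates. At 10 to 20% non-completion the trigger is unreachable in about 1 to 9% of cohorts; 35% and 52% require rates of one third and 40%. Patients entering after a third DLT are at most six, and on average about one or fewer per cohort over the DLT rates tabulated.

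It would go too far to say that two DLTs already settle the matter: 2 of 9 does not meet the last limit, so only a count of three satisfies all four.

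**What to change.** Reconcile the suspension trigger in 12.5 and 4.1.1 with the DLT limits in 12.5, so that a DLT count already meeting every stated limit brings the existing formal review forward instead of waiting for six completers. This adds no new limit and leaves the decision at the review with those already named in 12.5.

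The sponsor should also state:

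- what happens when fewer than six of the nine complete two cycles for any reason, including progression and withdrawal as well as toxicity;
- whether a patient who stops one drug and continues the other counts as completing;
- how the requirement to modify or stop when a limit is met fits with the option, listed just after it, of continuing unchanged.

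The cost is a few sentences in two sections, with no new committee, data or patients. The downside is that in a toxic cohort the review rests on fewer treated patients, who would otherwise inform the choice among modifying, stopping and continuing.

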13 CORRELATIVE DATA ANALYSIS

Biomarker Analyses: Pre- and post-treatment levels and changes from pre- to post-treatment in biomarkers will be summarized overall and by response and 6-month PFS categories using summary statistics (e.g., mean or median, with dispersion measures, and using transformed values as appropriate). Depending on the number of responses, logistic regression models may be used to compare response rates across pre-treatment biomarker levels. Proportional hazards models may be used to examine progression-free survival and overall survival across biomarker levels.

14 ETHICAL AND REGULATORY STANDARDS

14.1 Ethical Principles

This study will not be initiated until the protocol and informed consent document(s) have been reviewed and approved by a properly constituted Institutional Review Board (IRB) or Independent Ethics Committee (IEC). Each participant (or legal guardian) shall read, understand, and sign an instrument of informed consent prior to performance of any study-specific procedure. It is the responsibility of the investigator to ensure that the participant is made aware of the investigational nature of the treatment and that informed consent is given.

The Investigator is responsible for the retention of the participant log and participant records; although personal information may be reviewed by authorized persons, that information will be treated as strictly confidential and will not be made publicly available. The investigator is also responsible for obtaining participant authorization to access medical records and other applicable study specific information according to Health Insurance Portability and Accountability Act regulations (where applicable).

This study will be conducted in compliance with all applicable laws and regulations of the state and/or country and institution where the participant is treated. The clinical trial should be conducted in accordance with the ethical principles embodied in the Belmont Report: Ethical Principles and Guidelines for the Protection of Human Subjects of Research, consistent with good clinical practice and the applicable regulatory requirements and according to the guidelines in this protocol, including attached appendices.

14.2 Informed Consent

The Investigator (or IRB specified designee) is responsible for obtaining written consent from each participant or the participant's legally authorized representative in accordance with applicable GCP guidelines using the approved informed consent form, before any study specific procedures (including screening procedures) are performed. The informed consent form acknowledges all information that must be given to the participant according to GCP guidelines, including the purpose and nature of the study, the expected efficacy and possible side effects of the treatment(s), and specifying that refusal to participate will not influence further options for therapy. Any additional information that is applicable to the study must also be included. Additional national or institutionally mandated requirements for informed consent must also be adhered to. The participant should also be made aware that by signing the consent form, processing of sensitive clinical trial data and transfer to other countries for further processing is allowed.

The Investigator shall provide a copy of the signed consent form to the participant and the signed original shall be maintained in the Investigator File. A copy of the signed consent form must be filed in the participant file. At any stage, the participant may withdraw from the study and such a decision will not affect any further treatment options.

15 STUDY RESPONSIBILITIES

15.1 Data Collection

Data entry into the database is to be completed in a timely fashion (within 30 days) after the participant's clinic visit. If an AE is considered serious it is captured on both the Adverse Event page and the Serious Adverse Event Source Form, which is handled in an expedited fashion.

Data management activities will be performed using eClinical. eClinical is a suite of software tools that enables the collection, cleaning and viewing of clinical trial data. CRS data management will design the study-specific database and facilitate its development by the eClinical Information Technology team. Once the database design is approved by the Investigator, Statistician, and Clinical Research Coordinator, the database will be put into production and data entry can begin. Data can be entered and changed only by those with the rights to do so into the eCRFs (via the EXPeRT Module). eClinical is compliant with all relevant technical aspects of relevant GCP guidelines.

- The system can generate accurate copies of stored data and audit trail information in human readable form.
- System access is limited to authorized individuals through the controlled assignment of unique ID and password combinations.
- The system is designed to periodically force users to change their passwords and verifies that user ID and password combinations remain unique.
- The system automatically generates a permanent time-stamped audit trail of all user interactions.

When data entry is complete, data management will review the data and will query any missing, incomplete, or invalid data points for resolution by the Clinical Research Coordinator and Investigator. Once all queries have been resolved, the data can be released to the statistician for analysis.

15.2 Maintenance of Study Documents

Essential documents will be retained per RPCI's policy for 6 years from the study termination date. These documents could be retained for a longer period, however, if required by the applicable local regulatory requirements or by an agreement with RPCI.

16 ADMINISTRATIVE RULES

16.1 Revisions to the Protocol

RPCI may make such changes to the protocol as it deems necessary for safety reasons or as may be required by the U.S. FDA or other regulatory agencies. Revisions will be submitted to the IRB/ERC for written approval before implementation.

16.2 Termination of the Study

It is agreed that, for reasonable cause, either the RPCI Investigators or the Sponsor, may terminate this study, provided a written notice is submitted within the time period provided for in the Clinical Trial Agreement. In addition, RPCI may terminate the study at any time upon immediate notice if it believes termination is necessary for the safety of participants enrolled in the study.

16.3 Confidentiality

Any data, specimens, forms, reports, video recordings, and other records that leave the site will be identified only by a participant identification number (Participant ID, PID) to maintain confidentiality. All records will be kept in a limited access environment. All computer entry and networking programs will be done using PIDs only. Information will not be released without written authorization of the participant.

2. INFORMED CONSENT

- Informed consent must be obtained by the **site Investigator/designee** from any participants wishing to participate, **prior to any study specific procedures.**
- An informed consent template is provided by RPCI and can be amended to reflect institutional requirements.
- All consent changes **must** be reviewed by RPCI Network Office prior to submission to the site IRB.
- The informed consent must be IRB approved.
- Always check that the most up to date version of the IRB approved consent is being used.
- Within 5 business days, notify the RPCI Network Office of all participant withdrawals or consent to limited study participation and appropriately document the discontinuation and the reason(s) why.

3. PARTICIPANT REGISTRATION

The participant completes the Gender, Race, and Ethnicity Form and this is placed in the study binder.

RPCI does not grant exceptions to eligibility criteria.

Phase 1 Protocol Registration Instructions

Contact the RPCI Network Monitor to verify that a slot is available in the open cohort when a participant has been identified. **Do not have the participant sign consent prior to verifying an open slot.**

- After the participant signs consent, the Subject Screening and Enrollment Log must be faxed or emailed to the RPCI Network Monitor within 1 business day. The RPCI Network Monitor

will confirm receipt of the Subject Screening and Enrollment Log and email the participant ID number.

- When the participant has met eligibility, a signed eligibility checklist and other requested documentation will be faxed or emailed to the RPCI Network Monitor.
- Within 1 business day of receipt of the eligibility check list, the RPCI Network Monitor will fax or email the cohort assignment and dose level.
- An email must be sent by the site to confirm receipt of the cohort assignment and to provide the planned treatment start date.

Phase 2 Protocol Registration Instructions

The Subject Screening and Enrollment Log must be faxed or emailed to the RPCI Network Office within 1 business day of the date the participant is consented. Once the Investigator has determined that eligibility has been met, complete the eligibility check list and fax or email it to the RPCI Network Monitor at [contact].

4. STUDY DEVIATIONS

- If a deviation has occurred to eliminate hazard, this must be reported to the RPCI Network, site IRB and any other regulatory authority involved in the study.
- ALL study deviations will be recorded on the **Study Deviation Log**.
- Participants inadvertently enrolled with significant deviation(s) from the study-specified criteria will be removed from the study, at the discretion of the Principle Investigator.

